6.7 Synopsis of the study per patient

	Inclusion V1 J0	Blood sample D8 (to 10)	Phone Call D15 (to 18)	Blood sample D22 (to 24)	Phone Call D31 (to 37)	V2 D43 (to 50)	V3 D85 (to 100)
Inclusion / exclusion criteria	x						
Epistaxis grids surrender	x		x		x	x	
Epistaxis grids collection	x					x	x
Consent Form signature	x						
Pregnancy Test	x						
Clinical examination (HR, BP)	x					x	x
ENT examination	x					x	x
Hémoglobinemia, serum ferritin	x					x	x
FK 506 dosage		x		x		x	
Treatment : protopic/placebo dispensation	x						
Product return						x	
Blood Cell transfusions collection	x					x	x
ESS questionnaire	x					x	x
SF36 Quality of life questionnaire	x					x	x
Concomitant treatment collection	x		x		x	x	x
Adverse events collection	x		x		x	x	x

Legend: D = day V = visit

Table 1: Synopsis of the study per patient

7 Intercurrent events

7.1 Definitions

7.1.1 Adverse event

An **adverse event** (AE) is any untoward medical occurrence in a patient or clinical investigation patient administered a pharmaceutical product and which does not necessarily have to have a causal relationship with this treatment.

An adverse event can therefore be any unfavourable and unintended sign (including an abnormal laboratory finding, for example), symptom, or disease temporally associated with the use of a medicinal product, whether or not considered related to the medicinal product.

7.1.2 Serious adverse event (SAE)

A **serious adverse event** (SAE) is any untoward medical occurrence that at any dose:

- Results in death
- Is life-threatening (*the term "life-threatening" in the definition of "serious" refers to an event in which the patient was at risk of death at the time of the event ; it does not refer to an event which hypothetically might have caused death if it were more severe*)
- Requires in-patient hospitalization or prolongation of existing hospitalization
- Results in persistent or significant disability/incapacity
- Is a congenital anomaly/birth defect
- Is a medically significant event:

Medical and scientific judgment should be exercised in deciding whether expedited reporting is appropriate in situations, such as important medical events that may not be immediately life-threatening or result in death or hospitalization but may jeopardize the patient or may require intervention to prevent one of the outcomes listed in the definition above.

The term "severe" is a measure of intensity, thus a severe adverse event is not necessarily serious. For example, "nausea of several hours" duration may be severe but may not be clinically serious.

For "TACRO" study, any tacrolimus blood concentration resulting > 5ng/ml and any sign of infection under treatment should be considered as medically significant event and reported immediately by the investigator to the sponsor as a SAE.

7.1.3 Intensity

The intensity of the event will be graded according to the following classification:

- Mild (grade 1): Discomfort noticed but no disruption of normal daily activity
- Moderate (grade 2): Discomfort sufficient to reduce or affect normal daily activity
- Severe (grade 3): Incapacitating with inability to work or perform normal daily activity
- Life-threatening (grade 4): Substantial risk of dying at time of event
- Death: (grade 5)

7.1.4 Adverse reaction

An adverse reaction implies at least a reasonable possibility of a causal relationship between a suspected medicinal product and an adverse event. An adverse reaction, in contrast to an adverse event, is characterised by the fact that a causal relationship between a medicinal product and an occurrence is suspected.

7.1.5 Reference document for the experimental drug

Reference document for the experimental drug n°1: Summary of Product Characteristics (SPC) for PROTOPIC 0.1% (tacrolimus).

7.2 Responsibilities of the investigator

7.2.1 Adverse Events reporting

All **adverse events (AE)** regardless of seriousness or relationship to Investigational Product that occurred **after the informed consent up to 30 days after the last study drug administration** are to be recorded in the AE pages of the Case Report Form (CRF). After this delay only fatal AE and adverse event related to the IMP must be recorded.

Whenever possible, symptoms should be grouped as a single syndrome or diagnosis. The investigator should specify the date of onset, intensity, action taken regarding trial medication, corrective therapy given, outcome of all adverse events and his opinion as to whether the adverse event can be related to the study drugs and/or to concomitant drugs.

All events that meet one or more criteria of seriousness will be reported as Serious Adverse Event.

7.2.2 General AE/SAE reporting rules:

Any episode of any grade of toxicities, related to a Serious Adverse Event must be reported as "Adverse Event" in the appropriate CRF pages.

Adverse events (serious or not) will not be recorded after the start of a new out-of-study treatment or after disease progression.

Planned hospital admissions or surgical procedures for an illness or disease which existed before the patient was enrolled in the study or before study drug was given are not to be considered SAEs unless the condition deteriorated in an unexpected manner during the study (eg surgery was performed earlier than planned).

All adverse events which meet grade 3, 4 and 5 criteria must be reported immediately to the sponsor.

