3.2 Secondary objectives

The secondary objectives are to evaluate:

4. Tolerance of tacrolimus nasal administration for 6 weeks, throughout the study.

5. Efficacy of the treatment on progress in the

- clinical parameters:
 - Nosebleed duration,
 - Number of nosebleeds,
 - Number of transfusions of red blood cells.
 - Quality of life
 - ESS = Epistaxis Severity Score

- biological parameters: hemoglobin and serum ferritin concentrations

These parameters will be evaluated at the end of the 6 weeks of treatment (V2) and at the end of 6 weeks of follow-up (V3).

6. Systemic absorption after nasal administration.

4 Methodology

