4.3.2 Secondary judgement criteria

1. Adverse Events (AE) and Severe Adverse Events (SAE) observed throughout the study (clinical examination, epistaxis grids, ENT examination at each visit before and after the treatment). Additionally, all patients are contacted by phone after 15 and 30 days of treatment in order to collect data on tolerance and observance of the treatment.
2. Clinical efficacy criteria:
 - Nosebleed duration will be evaluated by the nosebleed monitoring grids completed by the patient (Appendix 1), collected at inclusion (V1): observation of the nosebleeds in the 6 weeks prior to inclusion, at the end of the treatment (V2): observation of the nosebleeds in the 6 weeks during treatment, and at the end of the study (V3): observation of the nosebleeds in the 6 weeks after the end of the treatment.
 - Progress in the number of nosebleeds. This criterion will be evaluated by the nosebleed monitoring grids completed by the patient (Appendix 1) collected at inclusion (V1): observation of the nosebleeds in the 6 weeks prior to inclusion, at the end of the treatment (V2): observation of the nosebleeds in the 6 weeks during treatment, and at the end of the study (V3): observation of the nosebleeds in the 6 weeks after the end of the treatment.
 - Comparison of the number of red blood cell transfusions between inclusion (V1) (collected over 6 weeks before treatment), the end of the treatment (V2) (collected over 6 weeks of treatment) and at the end of the study (V3) (collected over 6 weeks after the end of the treatment).
 - Progress in the scores obtained in the SF36 quality of life questionnaire

completed at inclusion (V1), at the end of the treatment (V2) and at the end of the study (V3).

- Progress in the ESS (Epistaxis Severity Score) using data from the specific questionnaire (Appendix 2) completed at inclusion (V1), at the end of the treatment (V2) and at the end of the study (V3).

Biological efficacy criteria: progress in hemoglobin and serum ferritin concentrations between inclusion (V1) and the end of the treatment (V2) and at the end of the study (V3).

3. Systemic absorption, after 1, 3 and 6 weeks of nasal administration, will be evaluated by a tacrolimus dosage in the blood at the end of the treatment.

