6.5 Visit at the end of the treatment, V2 = at day 43 (up to day 50 tolerated)

The patients will be seen in consultation, in the Reference center or skill center for HHT.

The following examinations/consultations will take place:

- Clinical examination including blood pressure and heart rate.
- Collection of the nosebleed grids completed by the patients during the 6 weeks of treatment (Appendix 1: Nosebleed monitoring grid), if not completed on line. These grids include monitoring of treatment administrations.
- The ESS questionnaire is completed by patient (Appendix 2).
- New nosebleed grids will be given to the patients for ENT monitoring during the next 6 weeks (Appendix 1: Nosebleed monitoring grid), if not completed online.
- The number of red blood cell transfusions received by the patient in the last 6 weeks will be noted.
- Patients will return the product, it will be transmitted to the hospital pharmacy.
- A set of biological blood samples (2 x 5 mL tubes) is collected: hemoglobinemia and serum ferritin.
- A blood sample is collected (4 mL on EDTA) for tacrolimus dosage.
- An SF36 quality of life questionnaire will be given to patients for completion.
- Monitoring and collection of any adverse events.
- Concomitant treatments will be noted.

6.6 Visit after 6 weeks follow-up, V3 = at day 85 (up to day 100 tolerated)

The patients will be seen in consultation, in the Reference center or skill center for HHT.

The following examinations/consultations will take place:

- Clinical examination including blood pressure and heart rate.
- Collection of the nosebleed grids completed by the patients during the 6 weeks' follow-up after the treatment (Appendix 1: Nosebleed monitoring grid), if not completed online.
- The ESS questionnaire is completed by the patient (Appendix 2).
- The number of red blood cell transfusions received by the patient in the last 6 weeks will be noted (as noted by the patient on the nosebleed grids).
- A set of biological blood samples (2 x 5 mL tubes) is collected: hemoglobinemia and serum ferritin.
- An SF36 quality of life questionnaire will be given to patients for completion.
- Monitoring and collection of any adverse events.

- Concomitant treatments will be noted.

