7.2.3 SAE declaration

All defined **Serious Adverse Events (SAEs)** occurred **after the informed consent up to 30 days after the last study drug administration**, whether or not ascribed to the study, will be recorded in the Serious Adverse Event pages. After this delay only fatal SAE and SAE related to the IMP must be recorded.

Serious Adverse Event (serious or not) will not be recorded after the start of a new out-of-study treatment or after disease progression (fatal event excluded)

All Serious Adverse Events must also be reported on the Adverse Event page of the CRF.

In a case of Serious Adverse event The Investigator must immediately:

- **SEND, by fax, the SAE pages to**

**SAFETY DESK:
[contact]**

All SAE forms must be dated and signed by the responsible Investigator or one of his/her authorized staff Members.

- Attach the photocopy of all examinations carried out and the dates on which these examinations were performed. Care should be taken to ensure that the patient's identity is protected and the patient's identifiers in the Clinical study are properly mentioned on any copy of source document. For laboratory results, include the laboratory normal ranges.
- Follow up of any Serious Adverse Event that is fatal or life threatening should be provided within one calendar week.

For serious adverse events, the following must be assessed: relationship to test substance, action taken, and outcome to date. The relatedness with concomitant treatment must also be evaluated. The Causality is initially assessed by the investigator. For serious adverse events, causality can be one of two possibilities:

- **Unrelated**
- **Related**

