9.2.2.5 Analysis of the secondary judgement criteria

All AE and SAE will be coded with MedDRA. Each adverse event observed between inclusion and the end of follow-up will be listed by frequency in each group. Then, the percentage of patients with at least one adverse event, or at least one severe adverse event will be computed and compared between the 2 groups. A list and verbatim of severe adverse events will be provided. All analyses will be performed on the safety population.

Efficacy criteria:

- The total duration of nosebleeds will be presented in each group for the 3 periods (6 weeks before treatment, 6 weeks of treatment, 6 weeks' follow-up after treatment). The relative evolution in duration of nosebleeds will be computed by subtracting the baseline value from the V2 value (end of treatment) and the V3 value (end of study). The delta from inclusion (V3/V1 & V2/V1) in total duration will be compared between the 2 groups using student t-tests (or

Mann-Withney tests in case of non normality). Mixed models will be produced to compare evolution between the groups.

- The number of nosebleeds will be presented in each group for the 3 periods (6 weeks before treatment, 6 weeks of treatment and 6 weeks' follow up after the end of treatment). The relative evolution in duration of nosebleeds will be computed by subtracting the baseline value from the V2 value (end of treatment) and the V3 value (end of study). The delta (V3/V1 & V2/V1) in number will be compared between the 2 groups using student t-tests (or Mann-Withney tests in case of non normality). Mixed models will be produced to compare evolution between the groups.
- The number of red blood cell transfusions will be presented in each group for the 3 periods (6 weeks before treatment, 6 weeks of treatment, 6 weeks' follow-up after treatment). The relative evolution in the number of red blood cell transfusions will be computed by subtracting the baseline value from the V2 value (end of treatment) and the V3 value (end of study). The delta (V3/V1 & V2/V1) in number of red blood cell transfusions will be compared between groups using student t-tests (or Mann-Withney tests in case of non normality). Mixed models will be produced to compare the evolution between groups.

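### Sections 7.2.1 and 7.2.3 limit full AE recording to 30 days after each patient's last application, while the AE objective, V3 procedures and analysis cover any AE to day 85

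*Combined protocol and SAP*

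**What the plan says.** Section 7.2.1 sets the period for recording every AE as "after the informed consent up to 30 days after the last study drug administration". Beyond that, "After this delay only fatal AE and adverse event related to the IMP must be recorded". Section 7.2.3 sets the same period for SAEs and continues: "After this delay only fatal SAE and SAE related to the IMP must be recorded".

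Other parts of the plan carry no such limit:

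- Secondary objective, 3.2: "Tolerance of tacrolimus nasal administration for 6 weeks, throughout the study".
- Criterion, 4.3.2: "Adverse Events (AE) and Severe Adverse Events (SAE) observed throughout the study".
- V3 procedures, 6.6: "Monitoring and collection of any adverse events". Table 1 in 6.7 also marks AE collection at V3.
- Analysis, 9.2.2.5: "Each adverse event observed between inclusion and the end of follow-up will be listed by frequency in each group". The proportions of patients with any AE and with any severe AE are then compared between arms on the safety population. No allowance for observation time is stated.

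Section 4.5 keeps patients who stop treatment, including for intolerance, on the planned follow-up schedule.

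**The concern.** An investigator at V3 who learns of a non-fatal event on day 75, judged unrelated, has two incompatible instructions. Section 6.6 says to collect it; 7.2.1 says it need not be recorded for a patient whose last application was on day 42. Centers may settle this differently.

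If 7.2.1 and 7.2.3 prevail, the full recording period is tied to each patient's own last application. A patient who stops early for good then has a shorter period than a completer, although both attend V3 and both enter the same safety tables. After the cut-off, whether an event enters the data depends on a causality judgement. That is a weak filter here, because 2.2 describes the safety of nasal administration as unknown and because 9.2.2.5 tabulates all AEs, not only related ones.

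**Working it through.** The documents give no figure for the length of the AE period, so there is none to reproduce. The check is calendar arithmetic.

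**Inputs**

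- Day 1 is the first day of treatment: 6.3 places day 15 at 14 days after the start.
- Treatment lasts 42 days (9.2.1.2), so a completer's last application is on day 42.
- Full recording ends 30 days after the last application (7.2.1, 7.2.3).
- V3 is on day 85, tolerated to day 100 (6.6).

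**Formulas.** For a last application on day s, full recording ends on day s + 30. Uncovered days to V3 = V3 − (s + 30). Share of the time after stopping that is uncovered, with V3 on day 85 = (55 − s)/(85 − s).

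| Last application (day) | Full recording ends (day) | Uncovered to day 85 | Share of time after stopping | Uncovered to day 100 |
|---|---|---|---|---|
| 8 (assumed) | 38 | 47 | 47/77 = 61% | 62 |
| 14 (assumed) | 44 | 41 | 41/71 = 58% | 56 |
| 21 (assumed) | 51 | 34 | 34/64 = 53% | 49 |
| 25 (assumed) | 55 | 30 | 30/60 = 50% | 45 |
| 42 (completer) | 72 | 13 | 13/43 = 30% | 28 |

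The share exceeds one half when 55 − s > (85 − s)/2, that is, for s below 25. Uncovered here means uncovered for non-fatal events judged unrelated. The early-stop rows describe permanent stops only. If treatment is resumed, as 4.5 and 6.2.2 allow, the last application moves later and the gap shrinks.

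**Effect on each summary in 9.2.2.5**

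1. *Listing of events by frequency.* Affected. Each uncovered day removes non-fatal unrelated events from the count, and the number of uncovered days differs between patients.
2. *Proportion with any AE.* Little affected among patients who stopped for intolerance, because the event that made them stop is already recorded. The same holds for a stop triggered by a tacrolimus level above 5 ng/mL, which 7.1.2 makes an SAE. What remains is late unrelated events in patients with no earlier AE, such as completers or those who stopped for logistical reasons.
3. *Proportion with any severe AE* (4.3.2 uses that word to expand SAE). Affected where the stopping event was neither severe nor serious and a later unrelated one would have been.

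**The case against.** The case against giving this much weight has five parts.

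- Recording does not stop at 30 days. Fatal and product-related events are kept, and related events bear most directly on tolerance.
- Loss is not certain. Section 6.6 and Table 1 call for AE collection at V3, and data are missed only if sites let 7.2.1 and 7.2.3 override them.
- Patients who stop for intolerance are already counted as having an AE, so a shorter period afterwards cannot remove them from that proportion.
- Differential stopping is not documented. Section 2.2 describes burning as transient and usually not leading to interruption, treatment may be reintroduced (6.2.2), and 2.3 allows that the ointment form itself may be poorly accepted, which could affect both arms.
- Thirty days is a reasonable pharmacological margin: with the 75-hour half-life in 1.3.4, 30 × 24 / 75 = 9.6 half-lives. Even a patient who stops on day 1 is covered to day 31, the nominal cut-off for the safety committee's data on each new cohort.

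All five points stand, and they narrow the issue. They do not remove it: the recording rule and the analysis period still disagree, and nothing says which governs.

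A reader might go further and infer that the active arm will look safer than it is, since 11.2 expects burning or irritation in about half of patients and those who stop are observed for less time. The documents do not support that. They give no stop rates by arm. A calculation that assumes more active-arm stops and counts only unrelated events leaves out the AE that caused each stop.

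**Conclusion.** The conflict is real and should be reconciled. If 7.2.1 and 7.2.3 are applied as written, non-fatal AEs and SAEs judged unrelated are unrecorded for 13 days before day 85 in a completer (28 days if V3 falls on day 100). The gap is longer in a patient who stops early and permanently: 47 days to day 85 for an assumed last application on day 8. It exceeds half of the time after stopping only for a last application before day 25.

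The consequence is uneven observation time, and dependence on a causality judgement, in the event-frequency listings and the severe or serious AE comparison. The effect on the proportion with any AE is small among patients who stopped for intolerance. Neither the direction nor the size of any between-arm bias can be stated. The conclusion assumes day 1 is the first application and that sites follow 7.2.1 and 7.2.3 over 6.6. If they follow 6.6, nothing is lost, but the text still needs correcting so that all sites do the same.

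**What to change.** In 7.2.1 and 7.2.3, replace the period "after the informed consent up to 30 days after the last study drug administration" with: from informed consent to V3 (or day 85 if V3 is missed), or to 30 days after the final application, whichever is later. Keep the fatal-or-related rule for events after that point.

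This brings the recording rule into line with 3.2, 4.3.2, 6.6, Table 1 and 9.2.2.5, and removes the dependence on stop date that comes from the 30-day clock. It does not make every patient's period identical, since V3 may fall between day 85 and day 100. Nor does it address the separate rule in 7.2.2 ("Adverse events (serious or not) will not be recorded after the start of a new out-of-study treatment or after disease progression"), which 7.2.3 repeats for SAEs with fatal events excepted.

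The cost is a wording change in two sections and a few more unrelated AEs and SAEs to enter and report. No visit is added, because V3 already includes AE collection. The sample size is unaffected.

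### Sections 7.2.2 and 7.2.3 stop adverse-event recording at two undefined points, while 6.6, Table 1 and 9.2.2.5 collect and analyse events to V3

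*Combined protocol and SAP*

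**What the plan says.** **The stop rule.** Section 7.2.2 says: "Adverse events (serious or not) will not be recorded after the start of a new out-of-study treatment or after disease progression". Section 7.2.3 says that serious events "will not be recorded after the start of a new out-of-study treatment or after disease progression (fatal event excluded"). The exemption for deaths appears only in 7.2.3.

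**Other duties in section 7.**
- 7.2.1 and 7.2.3 require all events, related or not, from consent to 30 days after the last dose. 7.2.1 continues: "After this delay only fatal AE and adverse event related to the IMP must be recorded". The 7.2.3 counterpart is: "After this delay only fatal SAE and SAE related to the IMP must be recorded".
- 7.2.2 also says: "All adverse events which meet grade 3, 4 and 5 criteria must be reported immediately to the sponsor". It sets no limit of time or treatment. Grade 5 is death (7.1.3).
- 7.1.2 says that "any sign of infection under treatment should be considered as medically significant event" and has it reported at once as an SAE, as it does for tacrolimus above 5 ng/mL.
- 7.2.4 requires every adverse event to be documented and its outcome followed.

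**Collection and analysis.** The first secondary criterion in 4.3.2 is "Adverse Events (AE) and Severe Adverse Events (SAE) observed throughout the study". Section 6.6 and Table 1 collect adverse events at V3 (D85, tolerated to D100) without condition. Section 9.2.2.5 says: "Each adverse event observed between inclusion and the end of follow-up will be listed by frequency in each group". It then compares the percentage of patients with at least one event between the arms, in the safety population.

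**Who stays in follow-up.** Patients who stop treatment (4.5, 9.2.1.1) and those who take a substitute treatment (9.2.2.6) are followed as planned.

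**The concern.** Recording would end at a time that depends on what happens to the patient after randomization. A patient who takes another treatment because the ointment irritates or fails could reach that point, and the chance of doing so may differ between tacrolimus and placebo. The patient would still attend V3, where one part of the protocol asks for adverse events and another forbids recording them.

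Tolerance is the first secondary objective, and section 2.2 says that the safety of nasal administration is unknown. The stop rule has no exception for drug-related events, which 7.2.1 keeps even after its 30-day limit. Because the triggers are undefined, two sites could also treat the same patient differently.

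**Working it through.** This is mainly a comparison of passages, with one piece of day arithmetic.

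**1. Are the triggers defined?** No. Neither phrase is explained, and neither occurs outside 7.2.2 and 7.2.3. Section 5.4 bars other experimental nosebleed drugs and authorizes all other necessary concomitant treatments, without saying whether any counts as out-of-study. The nearest wording is the substitute treatment in 9.2.2.6, which is not linked to section 7. Table 1 contains no assessment of progression.

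**2. What does the stop rule meet elsewhere?**

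| Provision | Event after a trigger | Relation to the stop rule |
|---|---|---|
| 7.2.4 | Documented, any grade | Conflict |
| 6.6, Table 1 | Collected at V3 | Conflict |
| 4.3.2, 9.2.2.5 | In the criterion and the analysis | Conflict |
| 7.2.1 | Required to last dose + 30 days, then if fatal or related | Tension, unless the stop rule is an unstated exception |
| 7.2.2, grade 3 to 5 | Reported immediately | Tension, unless reporting differs from recording |
| 7.1.2, infection under treatment | Reported as SAE | Tension if the patient is still on ointment |
| 7.2.3 against 7.2.2 | Deaths exempt in 7.2.3 only | The two stop sentences disagree |

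**3. Effect on the analysis.** The safety population is every patient with at least one application (9.2.1.3). A patient whose events go unrecorded stays in the denominator and counts as having no event in the missing period. With 24 patients per arm, all in the safety population, a patient whose only event falls after a trigger lowers that arm's percentage by 1/24 = 4.2 points. A patient with an event already recorded does not change this percentage, but the later events are missing from the listing by frequency.

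**4. Days lost to the stop rule.** These would be 85 − d, where d is the day of the trigger. The documents give neither d nor a rate for either trigger, and d could fall at any time after inclusion. No figure can be derived.

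**5. The 30-day window.** Inputs: day 1 is the first dose (6.3 calls D15 14 days after the beginning), 42 days of dosing (9.2.1.2), V3 at D85 with a limit of D100 (6.6).
- Last dose: D42. Window ends: 42 + 30 = D72.
- Gap to V3: 85 − 72 = 13 days. Gap to the limit: 100 − 72 = 28 days.
- If the last dose is D43, the window ends at D73 and the gaps are 12 and 27 days.

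In general the gap to D85 is 55 − L days for last dose on day L, so it is longer for patients who stop early. It concerns only non-fatal, unrelated events.

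**The case against.** The best defence is that 7.2.2 is headed as general reporting rules and can be read as an exception to 7.2.1, and that it says recorded where the grade 3 to 5 sentence says reported. Both readings are possible, so those two conflicts are better called tensions. Neither reading is stated, however, and neither settles the conflict with 7.2.4, 6.6, Table 1 and 9.2.2.5. Section 7.2.3 also requires every SAE to appear on the adverse-event page, so reporting without recording would be hard to operate.

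The reach of the rule may also be small. With no progression assessment, that trigger has no operational event, and authorized concomitant treatments may well not count as out-of-study. This stands: the documents do not show how often the rule would apply.

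A reader might infer more than the text supports:
- *That mild and moderate events have no other safeguard.* Section 7.2.4 has no grade limit, V2 and V3 collect events of any grade, and the Appendix 1 grid asks patients to list important events. A site might follow these instead of the stop rule.
- *That the DSMB's continuation decisions are undermined.* The numerical rules in 2.3 count treatment stops. Interruptions and their reasons are collected at the calls (6.3, 6.4), and 7.2 does not restrict this.
- *That the 30-day limit bans later recording.* It can be read as a minimum duty, so it is a misalignment only.
- *That the rule favours tacrolimus.* Nothing in the documents gives a direction.

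**Conclusion.** The concern holds as an internal inconsistency that should be fixed. Sections 7.2.2 and 7.2.3 state a rule which, if followed, removes events, including drug-related ones, from the comparison in 9.2.2.5 at a patient-specific time after randomization. The two sentences also disagree on deaths.

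That the passages conflict is certain. The practical impact is not: it depends on how sites read the triggers and how often they occur, and the documents settle neither. The percentage in step 3 is a scale per affected patient, not an estimate of bias. The only gap in days that can be derived is the secondary one, 13 days to V3 at D85 or 28 days to D100, assuming a full course with the last dose on D42.

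The primary endpoint rests on the nosebleed grids and is not affected.

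**What to change.** 1. Delete the sentences in 7.2.2 and 7.2.3 that end recording at a new out-of-study treatment or disease progression.
2. State in 7.2.1 and 7.2.3 that all AEs and SAEs are recorded for every included patient from consent to the V3 visit, or to last contact or withdrawal of consent if earlier, whatever the date of the last dose or the start of another treatment. Keep the rule on fatal and IMP-related events for the time after that point.

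Both steps are needed, since deletion alone leaves the gap from D72 to V3. Limiting the 9.2.2.5 analysis to the recorded period would also remove the conflict. It would, however, shorten an objective that covers the whole study and would still leave out related events.

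The cost is a protocol amendment under 11.6 and a few more AE and SAE forms. There are no new visits, because collection at V3 is already planned for everyone.

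A separate point: 5.4 withdraws a patient from the study at nasal surgery, while 4.6.1 and 9.2.2.6 maintain follow-up. These passages must be reconciled.
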